Statistical Considerations:	
This is a proof of concept feasibility study, so no power calculation is needed. Therefore, up to 35 subjects meeting inclusion/exclusion criteria will be recruited until 30 subjects have completed treatment. Descriptive statistics will be performed to explore changes in primary and secondary outcomes measures between baseline and end of treatment. The primary efficacy measure will be a reduction in the number of stress incontinence episodes/day. Secondary efficacy measures will include reduction in number of voids per day, volume of voids, 24 hour pad weight, responses to validated questionnaires, changes in UPP measures, changes in sexual function, and changes in pelvic floor muscles as measured by MRI.
 
Safety will be determined by the number and type of adverse events reported during treatment. Various imputation methods may be explored.

Study Intervention/Treatment:	
Participation in this study includes 5 in person study visits and two telephone and/or mailed questionnaire visits. Additional in person and/or telephone visits may be added as needed.
 
Study subjects will receive 3 mg of GTx-024 orally daily.

Table 1. Schedule of Measures.

	Screening Visit Days -21-0	Additional Screening Days -21-0	Visit 1. Baseline³ Week 0	Visit 2. Week 1 ± 3 days	Visit 3. Week 4 ± 3 days	Visit 4. Week 8 ± 3 days	Visit 5. Week 12 ± 3 days	Visit 6. Week 16 ± 7 days
	Clinic Visit	Clinic Visit	Clinic Visit	Phone Call	Clinic Visit	Clinic Visit	Clinic Visit	Phone Call and Mail
Consent	x							
Inclusion/Exclusion	x		x					
History			x					
Interview/Vital Signs	x		x		x	x	x	
Height/Weight	x				x	x	x	
24 hour Pad Weight	Instruct		x		x	x	x	
3 day Voiding Diary	Instruct		x		x	x	x	
Serum AST, ALT, Total Bilirubin	x				x	x	x	
Serum FSH ¹ ,	x							
CBC			x				x	
UA Dipstick (with culture as needed)	x		x				x	
Lipid Panel			x				x	
Testosterone Levels			x				x	
SHBG			x				x	
UPP			x				x	
Pelvic MRI		x					x	
Bladder Stress Test	x						x	
Mammogram ²		x						
Begin Daily ⁴ Treatment			x					
End Treatment							x	
Concomitant Meds	x		x	x	x	x	x	x
Adverse Events			x	x	x	x	x	x
HIV, Hep A, B, C Testing	x							
UDI-6; IIQ			x		x	x	x	x
PGI-S			x		x	x	x	x
MESA Questionnaire	x				x	x	x	x
PGI-I					x	x	x	x
FSFI Questionnaire			x		x	x	x	x
Bladder Scan PVR			x		x	x	x	
Ciprofloxacin 500 mg po (or equivalent)			x				x	
Focused Physical Exam			x				x	

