10. STATISTICAL CONSIDERATIONS

Since this is a proof of concept feasibility study, no power calculation is needed. Based on Dalton, 2011, 10-20% of patients may withdraw from the study before completing treatment. Therefore, we will recruit up to 35 patients meeting inclusion/exclusion criteria until 30 subjects have completed treatment. Descriptive statistics will be used to explore changes in primary and secondary outcomes measures between baseline and end of treatment. Although the primary efficacy measure will be a change in frequency of daily stress leaks between Baseline and Week 14 weeks, response to treatment will also consider secondary efficacy measures (change in frequency of voids per day, urine volume per void, change in 24 hour pad weight, responses to validated questionnaires, changes in UPP measures, changes in sexual function), and change in pelvic floor muscles as measured by MRI. Safety will be reported by the number and type of adverse events reported during treatment. No imputations for missing data will be conducted. There will be no adjustment for multiple testing.

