- Change in Patient Global Impression of Severity (PGI-S) Scale from Baseline to Week 12 will be computed and this change will be summarized with descriptive statistics (min, max, median, mean, standard deviation) and analyzed for a significant change from Baseline using the Exact Wilcoxon sign rank test.
- Patient Global Impression of Improvement (PGI-I) Scale at Week 12. Descriptive statistics, (min, max, median, mean, standard deviation) will summarize these scores.
- Change in total score on the Urinary Distress Inventory (UDI-6) from Baseline to Week 12 will be computed and this change will be summarized with descriptive statistics (min, max, median, mean, standard deviation) and analyzed for a significant change from Baseline using the Exact Wilcoxon sign rank test.
- Change in total score on the Incontinence Impact Questionnaire (IIQ-7) from Baseline to Week 12 will be computed and this change will be summarized with descriptive statistics (min, max, median, mean, standard deviation) and analyzed for a significant change from Baseline using the Exact Wilcoxon sign rank test.
- Change in total score on the Female Sexual Function Index (FSFI) as well as the change in subdomain scores: libido, arousal, lubrication, orgasm, satisfaction, and pain from Baseline to Week 12 will be computed and these changes will be summarized with descriptive statistics (min, max, median, mean, standard deviation) and analyzed for a significant change from Baseline using the Exact Wilcoxon sign rank test.

- Changes in pelvic floor muscles from Baseline to Week 12 will be summarized with descriptive statistics (min, max, median, mean, standard deviation) and analyzed for a significant change from Baseline using the Exact Wilcoxon sign rank test.
- Qualitative changes in pelvic muscles will be described as decreased, increased or no change at Week 12 relative to Baseline.

Exploratory Analyses

Changes from baseline to each of the assessment times prior to Week 12 for the above endpoints will be explored, described and tested for significance using the same analytical methods noted for the primary and secondary objectives above. Durability treatment will be assessed by evaluating changes in study measures between week 12 and 16 (end of study). There will be no adjustment for multiple testing, nor will any data be imputed.

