Repeated measures (mixed models) will be used to examine the change over time by incorporating all available assessment times to test for a significant non-zero slope over time and estimate that slope and its standard error.

Various imputation methods may be explored if any of the above analyses indicate promise for the compound in the treatment of SUI. These imputation methods may allow for better estimation of effect size and consequently sample size estimation in future trials.

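### The plan gives three incompatible rules on imputing missing data, and the most detailed one lets a favourable result decide whether imputed effect sizes are produced for future trials

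*Combined protocol and SAP*

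**What the plan says.** The plan speaks about imputation in four places.

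- Section 10, Statistical Considerations: "No imputations for missing data will be conducted".
- Section 10.1, Exploratory Analyses: "There will be no adjustment for multiple testing, nor will any data be imputed".
- Section 10.1, at the end of the same subsection: "Various imputation methods may be explored if any of the above analyses indicate promise for the compound in the treatment of SUI". The purpose follows directly: "These imputation methods may allow for better estimation of effect size and consequently sample size estimation in future trials".
- Section 1, Protocol Summary, Statistical Considerations: "Various imputation methods may be explored", with no condition attached.

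On expected loss, Section 10 says that "10-20% of patients may withdraw from the study before completing treatment" and that "we will recruit up to 35 patients meeting inclusion/exclusion criteria until 30 subjects have completed treatment". The primary analysis in Section 10.1 is the change from Baseline to Week 12 in average daily stress episodes, tested with an exact Wilcoxon signed rank test. Section 10.1 also plans a mixed model on all visits, whose stated output is a slope over time and its standard error.

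**The concern.** An analyst cannot follow all of these sentences at once. The most detailed of them ties a missing-data analysis to the result. Sensitivity to withdrawal matters whichever way the result falls, and arguably most when it is equivocal. An estimate produced only when the data already look good is a selected estimate, and this one is meant for sizing future trials, where an inflated effect leads to too few subjects. Two further freedoms add to this: promise has no threshold, and no imputation method is named, so both would be settled after the data are seen.

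**Working it through.** **1. The rules side by side**

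| Place | Rule | Depends on results? |
|---|---|---|
| Section 10 | No imputation | No |
| Section 10.1, Exploratory Analyses, first paragraph | No imputation | No |
| Section 10.1, Exploratory Analyses, last paragraph | Imputation may be explored if any analysis shows promise | Yes |
| Section 1, Protocol Summary | Imputation may be explored | No |

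That makes three positions: never, if promising, and freely.

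**2. How much is expected to be missing**

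The plan's only sample-size figure is 35 recruited for 30 completers. With withdrawal rate w, the number needed is 30/(1 - w):

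- w = 10%: 33.3, so 34
- w = 14.3%: 35
- w = 20%: 37.5, so 38

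The figure of 35 is therefore reproduced within the stated range, but not at its upper end, where 35 × 0.80 = 28 complete. Expected withdrawals from 35 are 3.5 to 7, or about 4 to 7 women. Section 7.2 points to Visit 6 of Table 1 for the measures to obtain from early withdrawals. Visit 6 is a telephone and mail contact without a voiding diary, so as written a withdrawing woman need not supply primary-endpoint data. The default Week 12 change then uses only women with a Week 12 diary.

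**3. How many tests could show promise**

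Section 10.1 lists these Week 12 signed rank tests:

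- primary endpoint (1)
- voids, volume per void, urethral closure pressure, pad weight, MESA, PGI-S, UDI-6 and IIQ-7 (8)
- FSFI total and six subdomains (7)
- at least one MRI measure (1)

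Total: 1 + 8 + 7 + 1 = 17, before the tests at earlier visits.

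The plan states no alpha, so two-sided 0.05 is assumed, or 0.025 in the favourable direction. With no true effect and independent tests, the chance of at least one favourable result is 1 - 0.975^17 = 0.35. With correlation 0.5 between endpoints (assumed), simulation gives about 0.20.

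**4. Size of the selection**

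The plan gives no effect size or SD, so these are assumptions: 28 completers, normally distributed changes, and an exact signed rank test. For the any-of-17 reading, every endpoint has the same true standardised change and correlations run from 0 to 0.5. The estimate is the mean primary change divided by the trial's own SD, averaged over simulated trials that meet the condition. It stands in for an imputed estimate from the same women.

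| True change | Promise = significant primary result | Promise = any of 17 tests |
|---|---|---|
| 0.2 | about 0.50 | about 0.21-0.28 |
| 0.5 | about 0.61 | about 0.52 |

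The 0.52 is nearly all ordinary small-sample bias in a standardised mean, not selection: 0.5 / (1 - 3/(4 × 27 - 1)) = 0.514.

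Required sample size varies as 1/(standardised change)². A trial planned on the selected estimate would therefore get this share of the subjects it needs:

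- Significant primary result: (0.2/0.50)² = 16%, and (0.5/0.61)² = 67%.
- Any of 17 tests: (0.2/0.21)² = 91% down to (0.2/0.28)² = 51%, and (0.5/0.52)² = 92%.

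**The case against.** The imputation is optional and exploratory, in a single-arm proof-of-concept study with no power calculation. The unimputed Week 12 result is reported whatever happens. Carrying any effect size forward because a trial looked promising selects in the same way, so deleting the trigger does not remove that wider selection. All of this stands, and it keeps the point modest.

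Three stronger readings are tempting and do not hold.

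- A reader might infer that the plan allows imputation only after a favourable result. That is true of Section 10.1 alone, since the Protocol Summary sets no condition.
- A reader might infer that withdrawals go unexamined when results are unfavourable. The mixed model is planned unconditionally and uses partial data from women who leave. What remains is that its stated target is a slope. A Week 12 change could be read from it only by assuming a straight line over time, and the plan does not say that this will be done.
- A reader might infer that the planning effect size would always be badly inflated. The large figures apply only if promise means a significant primary result. The literal wording covers any analysis, and a condition so easily met selects only weakly on the primary endpoint. Nor is the chance of a spurious trigger 1 - 0.95^17 = 58%: that counts significant worsening, which is not promise.

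Setting withdrawals to no change is itself a simple imputation and one choice among several. Dropping imputation altogether would also remove the contradiction, but would leave the Week 12 estimate resting only on women with Week 12 diaries.

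**Conclusion.** The point holds as an inconsistency combined with a result-dependent step. It is worth correcting, but it does not threaten the primary analysis. Sections 1, 10 and 10.1 cannot all be followed. Under Section 10.1, imputed estimates intended for future planning appear only after an undefined favourable finding. No unconditional Week 12 estimate accounts for the 10-20% expected to withdraw.

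The documents do not fix the size of the selection. On the assumptions above it ranges from negligible (any-of-17 reading with a true change of 0.5) to a planning estimate about 2.5 times the truth (0.50/0.2, primary-result reading with a true change of 0.2). That so much turns on an undefined word is itself a reason to remove it.

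**What to change.** Reconcile the four sentences in Sections 1, 10 and 10.1, and delete the result-dependent trigger. State one rule: the primary test uses observed data without imputation and, whatever its result, the Week 12 change in daily stress episodes will also be estimated in two ways:

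- from the repeated-measures model already planned, with visit as a category and all available visits included;
- as a conservative sensitivity analysis, with women who withdraw set to no change from baseline.

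Because the second estimate is a form of imputation, the blanket exclusions must be reworded to cover the primary analysis only. Any further imputation method should be named in advance and run regardless of results.

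The cost is wording in three sections and two extra estimates from data already collected. The downside for the sponsor is that the effect size taken into future planning may be less favourable.

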11. QUALITY CONTROL AND QUALITY ASSURANCE

Standard operating procedures are available for all activities relevant to the quality of this study. Designated personnel will be responsible for implementing and maintaining quality assurance and quality control systems to ensure that the study is conducted, and that data are generated, documented, and reported in compliance with the study protocol, GCP, and Good Laboratory Practice requirements as well as applicable regulatory requirements and local laws, rules, and regulations relating to the conduct of the clinical study.

An authorized Quality Assurance auditor will audit the study data and procedures at periodic intervals as indicated. Domestic or foreign regulatory authorities, the IRB/IEC, and a Sponsor-authorized auditor may request access to all study documentation for an on-site inspection or audit. The Investigator must notify GTx, Inc. of any regulatory authority inspections and forward copies of the inspection report to GTx, Inc.

Electronic data systems will be in accordance with applicable aspects of 21 CFR Part 11, ICH Guidelines, GCP, local laws and legislation, and the Health Insurance Portability and Accountability Act.

On-site Audits

At any time, quality assurance representatives of the Sponsor and/or regulatory bodies may visit the unit to carry out an audit of the study in compliance with regulatory guidelines and company policy. Such audits will require access to study records, documentation, and regulatory files. At all times, subject privacy will be of utmost importance and respected. Typically, sufficient notice will be given to the Investigator to prepare for the visit.

12. ETHICS/PROTECTION OF HUMAN SUBJECTS

12.1 ETHICAL CONSIDERATIONS

This clinical study will be conducted in accordance with the ethical principles that have their origin in the Declaration of Helsinki and in accordance with global regulations including 21 CFR 312.

The investigator is responsible for obtaining approval for this clinical study from the relevant IRB at the associated institution. The study will not begin until a favorable opinion of the IRB has been obtained. The investigator is responsible for complying with requirements imposed by the IRB and/or regulatory authority. Furthermore, the investigator will ensure that local regulations concerning data protection are followed. For ethical considerations, all patients will be required to sign a consent indicating their willingness to participate and that they have been fully informed of the risks and benefits of participation.

12.2 INSTITUTIONAL REVIEW BOARD/ INDEPENDENT ETHICS COMMITTEE

The protocol and the proposed ICF will be reviewed and approved by a properly constituted IRB/IEC before the study start. A signed and dated statement that the protocol and informed consent have been approved by the IRB/IEC will be given to GTx, Inc. or designee before study initiation. The signed IRB/IEC approval letter must identify the documents approved (i.e., list the Investigator's name, the protocol number and title, the date of the protocol, and the date of approval of the protocol and the informed consent document). Any advertisements used to recruit subjects must also be reviewed by the IRB/IEC. Clinical supplies will not be shipped to a site until a signed approval letter from the IRB/IEC has been received and a contractual agreement has been signed by both parties.

Prior to study start, the Investigator will be required to sign a protocol signature page confirming his/her agreement to conduct the study in accordance with these documents and all of the instructions and procedures found in this protocol and to give access to all relevant data and records to GTx, Inc. monitors, auditors, GTx, Inc. Clinical Quality Assurance representatives, designated agents of GTx, Inc., IRBs/IECs/Research Ethics Boards (REBs), and regulatory authorities as required.

12.3 PRE-STUDY DOCUMENTATION

The Investigator must provide GTx or its designee with the following documents prior to the enrollment of any subjects:

- Copy of the signed Investigator Agreement page
- Copy of the IRB/IEC approval letter for protocol and informed consent
- Completed, signed, and dated Form FDA 1572
- Current curricula vitae, licenses, and financial disclosures for the Investigator(s) and sub Investigators listed on the 1572
- Where applicable, list of IRB/IEC committee members and a statement of adherence to GCP
- Copy of approved informed consent document
- Executed clinical trial agreement
- Name, location, certification number, and date of certification of the laboratory to be used for laboratory assays and those of other facilities conducting tests. GTx or its designee must be notified if the central laboratory is changed or if any additional laboratory is to be used
- List of normal laboratory values (i.e., reference ranges and units of measure) for each central laboratory to be used during the study. GTx or its designee must be notified if normal values change

12.4 INFORMED CONSENT PROCESS

Eligible subjects will only be included in the study after providing written (witnessed, where required by law or regulation), IRB/IEC-approved informed consent.

The informed consent documents must be reviewed and approved by GTx or its designee and the investigative site IRB/IEC prior to the initiation of the study.

Each subject will receive an IRB/IEC approved informed consent document with study information. Subjects should be given ample time to read the information and the opportunity to ask questions. Informed consent must be obtained from each subject prior to performing any protocol-specific evaluations. The signed ICF will be retained with the study records and the subject will receive a copy of the signed informed consent for his/her records. The process of obtaining informed consent will be documented in the subject source documents.

The date when a subject's informed consent was actually obtained will be captured in their CRFs.

The Investigator (or designated staff) will explain the nature of the study as well as its risks and benefits to the subject (or the subject's legal representative).

12.5 SUBJECT CONFIDENTIALITY

Subject confidentiality is strictly held in trust by the participating Investigators, their staff, and the Sponsor(s) and their agents. This confidentiality is extended to cover testing of biological samples and genetic tests (if applicable) in addition to the clinical information relating to participating subjects.

The study protocol, documentation, data, and all other information generated will be held in strict confidence. No information concerning the study or the data will be released to any unauthorized third party without prior written approval of the Sponsor.

The study monitor or other authorized representatives of the Sponsor may inspect all documents and records required to be maintained by the Investigator, including but not limited to, medical records (office, clinic, or hospital) and pharmacy records for the subjects in this study. The clinical study site will permit access to such records.

12.6 PROTOCOL ADHERENCE

By signing the Form FDA 1572, the Investigator agrees to conduct the study according to the protocol and the FDA regulations set forth in 21 CFR Parts 50, 54, 56, and 312.

12.7 PERMISSION TO REVIEW SUBJECTS' SOURCE RECORDS

The Investigator agrees to allow the FDA and other regulatory agencies, individuals delegated by the IRB/IEC and Competent Authorities, and the Sponsor or its designee to have access to all the original documentation of the study, including the ICFs signed by the subjects enrolled into the study and the relevant subject medical files. The individuals who are given access to the documentation must take every reasonable precaution to keep the identity of the subjects and the proprietary information of the Sponsor as confidential information in accordance with relevant applicable legislation.

12.8 PROTOCOL AMENDMENTS

All amendments to the study protocol must be submitted to the IRB/IEC for written approval. The approval letter, signed by the IRB/IEC Chairperson, must refer specifically to the Investigator, the protocol number and protocol title, the protocol

amendment number, and the date of the protocol amendment. A copy of the approval letter and revised informed consent document (if applicable) must be sent to GTx or its designee. A protocol amendment may be implemented only after it has been approved by the IRB/IEC and has been approved by the appropriate regulatory authority. In the case of a protocol change intended to eliminate an apparent immediate hazard to subjects, the change may be implemented immediately, but the change must then be documented in a protocol amendment and approved as described above.

12.9 CHANGE IN INVESTIGATOR

If any Investigator retires, relocates, or withdraws from an investigation during the conduct of the study the responsibility for conduct of the study may be transferred to another appropriately qualified Investigator at the investigative site. GTx or its designee must be notified. An updated Form FDA 1572 must be submitted to GTx or its designee.

